5.1 Inclusion and exclusion criteria for research subjects

Inclusion Criteria:

- (1) Screened as positive for intrinsic capacity declines.
- (2) Decline in intrinsic capacity confirmed by in-depth assessment in any of the domains described as: MMSE < 27 (for cognition), SPPB ≤ 9 (for locomotion), MNA-SF < 12 (for vitality we used nutrition as a proxy), GDS-5 ≥ 2 (for psychology we used depression as a proxy) or any vision impairment.
- (3) Signed form of consent and willingly participate in the pilot study.

Exclusion Criteria:

- (1) Negative results in their intrinsic capacity decline screening.
- (2) Severe hearing problems as the study was conducted during COVID-19 pandemics period and relied on telecare or remote sessions of intervention.

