For the first question, predefined parameters such as sample size, capacity building, acceptance by community-dwelling older people (participants) and care providers were examined.

3. Research methods

Prospective randomized controlled study. A total of 2000 community-dwelling older persons aged 60 and above at-risk of functional loss in Chaoyang District of Beijing are recruited and randomly assigned to the intervention group (n=500) and control group (n=1500).

3.1. Primary Outcome Measure:

Feasibility of implementing the ICOPE program in China:

- 1) Sample size (to successfully recruit over 2,000 participants, 500 of whom were to be categorized in the intervention group)
- 2) Capacity building (at least 200 primary care providers to be fully trained and deployed in the pilot program)
- 3) Acceptance (reach more than 90% satisfaction with the pilot by both participants and providers).

3.2. Secondary Outcome Measures:

Independence - measured by the activities of daily living (ADL) 14-questionnaire scale, to assess the participant's physical function.

Cognition - measured by mini-mental status examination (MMSE) to assess the cognitive health of the participants.

Vitality - nutrition measured by mini-nutritional assessment- short form (MNA-SF) to assess the risk of malnutrition.

Mobility - measured by short physical performance battery (SPPB) to assess the risk of declining mobility.

Psychological health - measured by geriatric depression scale-five items (GDS-5) using a short set of questions to assess possible depressive symptoms.

4. Statistical methods and sample size

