4.1. Sample size calculation

At present, there is no specific local data to support the calculation of sample size.

Using all-cause death and falls as the endpoint events, based on previous literature and pre-experimental data, the percentage of decline in intrinsic ability in the community elderly population as the dependent variable ranged from 43.0% to 77.4%, and the incidence of all-cause death, falls and functional decline in the group with decline in intrinsic ability at 3-year follow-up was 16.4%, 55.3% and 64.8%, respectively, using PASS software, setting a two-sided $\alpha=0.05$ with 90% certainty, based on the above data, it was calculated that at least 58 people with all-cause death as the endpoint event of decline in intrinsic ability, 72 people with falls as the endpoint event, and 126 people with decline in function as the endpoint event were required, considering that the population included in this study was elderly, and based on previous studies, the proportion of decline in intrinsic ability was estimated to be 70%, and considering a 5% loss of follow-up rate, at least 190 elderly people. Therefore, a total of 380 individuals were included in the intervention and control groups (intervention community and control community).

This project plans to investigate and follow up with at least 2000 older people and intervene in more than 500 cases. Combined with the sample size calculation above, this project should meet the needs of sample size.

4.2. Statistical methods:

STATA will be used to establish the database and conduct statistical analysis.

The baseline data were collected, and the corresponding statistical methods were selected according to the data type to compare the basic clinical information of patients: if the data conformed to the normal distribution, it was expressed as the mean \pm standard deviation ($\pm s$),

and the independent sample t test was used for the comparison between the two groups; If the data does not conform to the normal distribution, it is expressed as the median (25th percentile, 75th percentile), and the Mann Whitney U test is used for the comparison between the two groups.

The intervention group and the control group were propensity matched, and the incidence of adverse health outcomes (all-cause death, falls, functional decline) and changes in quality of life (self-control, comparison between the two groups) were compared between the two groups.

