5.2 Randomization

A random number table (1-2000 random order) was established and managed by a dedicated person (who was only responsible for informing the number). The older person who met the enrollment conditions received random numbers according to the order of the random number table. The random number divided by 3 is an integer, and the remaining 1 is the control group, and the remaining 2 is the intervention group.

6. Research process

6.1 Data acquisition and observation indicators:

- (1) The elderly who met the inclusion criteria were included, and their demographic characteristics (gender, age, education, height, weight, BMI, smoking and drinking history) were recorded
- (2) Assessment of intrinsic ability: according to the screening tool for integrated care for older people (ICOPE) and the people-centered assessment guide issued by WHO, there are five dimensions in total, with 1 point for each dimension. Impairment in any dimension is defined as a decline in intrinsic ability. See Case Report Form (CRF) for the rating scale of each dimension.

Cognitive dimension: Mini Mental State Examination (MMSE), with a total score of 30 points. According to the education level of the research object, whether there is cognitive dysfunction is defined. Illiteracy ≤ 17 points, primary school level ≤ 20 points, secondary school level (including technical secondary school) ≤ 22 points, university level (including junior college) ≤ 23 points. Vitality: the mini nutritional assessment short form (MNA-SF) has

a total score of 14 points. A score of 12-14 defines normal nutritional status, 8-11 indicates malnutrition risk, and 0-7 indicates malnutrition.

Psychology: the total score of the geriatric depression scale 15 item (GDS-15) is 15 points, and a score of ≥ 5 points is defined as depression (Appendix 3). Or the Zung Depression Scale (SDS) was used for evaluation. Standard score = total score \times 1.25, take an integer, and a standard score > 50 points is considered as depression.

Exercise: the short physical performance battery test (SPPB), including the evaluation of sitting up test, gait speed test and balance test, has a full score of 4 points for each part, a total score of 12 points, and a score of ≤ 9 points is considered as physical function decline.

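### GDS-5 is the declared depression outcome and an entry test, but the data-collection section names GDS-15 or SDS instead; sections 5.1 and 6.1 also define cognitive decline differently

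*Combined protocol and SAP*

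**What the plan says.** **Depression.** Section 3.2 lists psychological health as a secondary outcome, "measured by geriatric depression scale-five items (GDS-5"). Section 5.1 uses the same scale at entry: "GDS-5 ≥ 2 (for psychology we used depression as a proxy"). Section 6.1 covers data acquisition. Under psychology it gives GDS-15, with 5 or more of 15 points counted as depression and a reference to Appendix 3. It then offers the Zung scale (SDS) as an alternative, with a standard score above 50 counted as depression. It does not mention GDS-5 and gives no rule for choosing between the two. Section 6.2 triggers its depression action on GDS-15 of 5 or more.

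**Follow-up.** Section 6.3 names ADL, a frailty scale, falls and death. It then plans re-assessment at 3 and 6 months in the intervention arm and at 6 months in the control arm, without listing instruments.

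**Cognition and the other domains.** Section 5.1 requires "Decline in intrinsic capacity confirmed by in-depth assessment" in at least one domain, with cut-offs "MMSE < 27 (for cognition), SPPB ≤ 9 (for locomotion), MNA-SF < 12 (for vitality we used nutrition as a proxy), GDS-5 ≥ 2" or impaired vision. Section 6.1 sets MMSE cut-offs by education: at most 17 (illiterate), 20 (primary), 22 (secondary) and 23 (university). It says "there are five dimensions in total, with 1 point for each dimension" and "Impairment in any dimension is defined as a decline in intrinsic ability". Its sensory dimension counts hearing loss as well as vision loss. Section 6.2 acts at MMSE below 24, SPPB below 9 and MNA-SF below 11.

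**The concern.** The section that tells sites what to record does not contain the scale that the outcome section declares. A site that follows 6.1 to the letter could finish without a 6-month GDS-5, or with GDS-15 for some people and SDS for others. These scales have different totals and cut-offs, so their scores cannot be pooled with GDS-5 or stand in for it. Six months is the only post-baseline re-assessment planned in both arms, so it is where a between-arm comparison of depression would have to be made. A reader of the results could not tell whether a reported depression result is the declared outcome.

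The MMSE difference matters less. Sections 5.1 and 6.1 both define decline in intrinsic capacity, but by different MMSE rules. Any count of people in decline, or any score of 1 point per dimension, therefore depends on which section is applied. The MMSE, SPPB and MNA-SF scores themselves do not change.

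**Working it through.** The plan gives no figure to reproduce on this point. The check sets the sections side by side and counts integer scores.

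**1. Depression scale by section**

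| Section | Purpose | Scale named |
|---|---|---|
| 3.2 | Declared secondary outcome | GDS-5 |
| 5.1 | Entry | GDS-5 ≥ 2 |
| 6.1 | Data acquisition | GDS-15 ≥ 5, or SDS standard score > 50 |
| 6.2 | Action in the intervention arm | GDS-15 ≥ 5 |
| 6.3 | Re-assessment | None |

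Sections 3.2 and 5.1 agree with each other. Sections 6.1 and 6.2 share GDS-15. No section links the two pairs, and the documents list no scale items, so they do not show whether GDS-5 can be derived from GDS-15 records.

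**2. MMSE: 5.1 against 6.1.** Entry under 5.1 is a score below 27, the set 0–26 (27 values). Subtracting the 6.1 impairment set at each education level gives:

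- Illiterate: 0–26 minus 0–17 leaves 18–26, and 26 − 17 = 9 values.
- Primary: 0–26 minus 0–20 leaves 21–26, and 26 − 20 = 6 values.
- Secondary: 0–26 minus 0–22 leaves 23–26, and 26 − 22 = 4 values.
- University: 0–26 minus 0–23 leaves 24–26, and 26 − 23 = 3 values.

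Scores 24–26 lie in all four sets. The reverse difference is empty: every score impaired under 6.1 also meets 5.1.

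**3. Other domains: 5.1 against 6.1.** SPPB agrees (9 or below in both). MNA-SF agrees (below 12 in 5.1; 0–11 is malnutrition or risk of it in 6.1). The two sections differ on cognition, on the depression scale, and on hearing, which 6.1 counts and the 5.1 list does not.

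**4. Entry against the 6.2 triggers**

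- MMSE: 0–26 minus 0–23 leaves 24, 25 and 26.
- SPPB: 0–9 minus 0–8 leaves 9.
- MNA-SF: 0–11 minus 0–10 leaves 11.

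These values qualify at entry, but 6.2 lists no domain-specific action for them.

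**5. Items needed to record GDS-5.** Section 3 plans 2,000 people, "randomly assigned to the intervention group (n=500) and control group (n=1500"). The allocation rule in 5.2 gives the intervention to numbers from 1 to 2,000 that leave remainder 2 on division by 3: (2,000 − 2)/3 + 1 = 667 numbers. The intervention arm is therefore taken as 500 to 667.

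- 6 months: 5 × 2,000 = 10,000 responses.
- Baseline, if GDS-5 was not taken from everyone: up to 5 × 2,000 = 10,000.
- 3 months, intervention arm, if used: 5 × 500 = 2,500 to 5 × 667 = 3,335.
- All three at the upper end: 10,000 + 10,000 + 3,335 = 23,335.

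**The case against.** **The CRF may settle it.** Section 6.1 refers to the CRF for the rating scales and to Appendix 3 for GDS-15, and neither is in the supplied text. A reader might infer that GDS-5 was never collected; the documents do not support that. GDS-5 is an entry test, and the CRF may list it at every visit. What stands is that the CRF could show what was used but would not reconcile 3.2 and 5.1 with 6.1 and 6.2.

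**The silence in 6.3 is general.** A reader might take it as a gap specific to depression. It is not: MMSE, SPPB and MNA-SF are also declared in 3.2 and also unnamed in 6.3. This objection holds, and the fix is widened to cover them.

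**The MMSE cut-offs may serve a different concept.** Section 6.1 speaks of cognitive dysfunction. But the same item equates impairment in any dimension with decline in intrinsic ability, so the two definitions do meet. A reader might go further and say that someone enrolled only on MMSE 24–26 must be unimpaired in every dimension under 6.1. That does not follow. Such a person may have non-severe hearing loss, which 6.1 counts, or may be positive on GDS-15 or SDS although below 2 on GDS-5. Only the cognitive dimension is certain.

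**The 6.2 triggers may be intended tiers.** This is possible. The general care plan in 6.2 may also cover people at the values without a listed action, so the text does not show that they go without care.

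**The consequences are limited.** Section 4.2 compares adverse outcomes and "changes in quality of life (self-control, comparison between the two groups"); it names neither depression nor a count of people in decline. This is correct and keeps the point below a fatal one. GDS-5 nevertheless remains a declared outcome in 3.2.

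**Conclusion.** The plan contradicts itself on its depression outcome. GDS-5 is declared and used for entry, the data-collection section specifies GDS-15 or SDS with no allocation rule, and the action trigger uses GDS-15. If 6.1 is followed as written, the declared outcome may be missing at 6 months or held on mixed scales. This should be corrected. It concerns one secondary outcome and does not affect the primary feasibility outcome (recruitment, training and satisfaction).

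The secondary point also holds. Between 3 and 9 MMSE score values, depending on education, are decline under 5.1 but not cognitive impairment under 6.1, and 24–26 disagree at every level. A person enrolled only on MMSE 24–26 can therefore be unimpaired under 6.1, unless hearing loss or the GDS-15 or SDS result counts them as impaired. The difference between the entry cut-offs and the 6.2 triggers is minor.

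These are counts of score values, not of people. The documents give no score distribution, so the share of participants affected cannot be computed, and no loss of power or dilution of effect is claimed. The conclusion about the depression outcome is conditional on sites following 6.1, because the CRF and Appendix 3 could not be checked.

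**What to change.** 1. Check the CRF and Appendix 3 for the scale used at each visit.
2. Make 3.2, 5.1, 6.1 and 6.3 name one depression outcome scale. GDS-5 is the one already declared. Collect it from everyone in both arms at baseline and 6 months, and drop the SDS alternative for the outcome. Do not pool GDS-15 or SDS totals with GDS-5.
3. State in 6.3 the instrument for every secondary outcome declared in 3.2, by arm and visit.
4. Reconcile 5.1, 6.1 and 6.2 on the MMSE, SPPB, MNA-SF and depression thresholds. This includes which depression score 6.2 acts on, so that naming an outcome scale does not leave that trigger without a score. The investigators decide the values and say whether separate tiers are intended.
5. If data are already collected, tabulate by arm and visit which scale each person has. Derive GDS-5 from GDS-15 only where item content and item-level records allow it, and treat it as missing otherwise.

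**Cost.** Wording, plus five items per person per visit where GDS-5 is not already recorded. For 2,000 people this is up to 10,000 responses at 6 months. Baseline should not be assumed free: 5.1 needs decline in only one domain, so someone may enter on SPPB or vision without a GDS-5, and up to another 10,000 responses could be needed. If the scale is also used at 3 months in the intervention arm, add about 2,500 to 3,335. These are planning figures, since 4.1 allows for more than 2,000 people and more than 500 in the intervention arm. No extra participants are needed. For data already collected, the cost is one table and an item-level check.

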5.2 Randomization

A random number table (1-2000 random order) was established and managed by a dedicated person (who was only responsible for informing the number). The older person who met the enrollment conditions received random numbers according to the order of the random number table. The random number divided by 3 is an integer, and the remaining 1 is the control group, and the remaining 2 is the intervention group.

6. Research process

6.1 Data acquisition and observation indicators:

- (1) The elderly who met the inclusion criteria were included, and their demographic characteristics (gender, age, education, height, weight, BMI, smoking and drinking history) were recorded
- (2) Assessment of intrinsic ability: according to the screening tool for integrated care for older people (ICOPE) and the people-centered assessment guide issued by WHO, there are five dimensions in total, with 1 point for each dimension. Impairment in any dimension is defined as a decline in intrinsic ability. See Case Report Form (CRF) for the rating scale of each dimension.

Cognitive dimension: Mini Mental State Examination (MMSE), with a total score of 30 points. According to the education level of the research object, whether there is cognitive dysfunction is defined. Illiteracy ≤ 17 points, primary school level ≤ 20 points, secondary school level (including technical secondary school) ≤ 22 points, university level (including junior college) ≤ 23 points. Vitality: the mini nutritional assessment short form (MNA-SF) has

a total score of 14 points. A score of 12-14 defines normal nutritional status, 8-11 indicates malnutrition risk, and 0-7 indicates malnutrition.

Psychology: the total score of the geriatric depression scale 15 item (GDS-15) is 15 points, and a score of ≥ 5 points is defined as depression (Appendix 3). Or the Zung Depression Scale (SDS) was used for evaluation. Standard score = total score \times 1.25, take an integer, and a standard score > 50 points is considered as depression.

Exercise: the short physical performance battery test (SPPB), including the evaluation of sitting up test, gait speed test and balance test, has a full score of 4 points for each part, a total score of 12 points, and a score of ≤ 9 points is considered as physical function decline.

Sensory: vision assessment (do you have vision loss that affects your normal life even after wearing glasses or surgery?); Hearing assessment (do you have hearing loss that affects your daily life?). If you answer yes to either question, you have a visual impairment or a hearing impairment.

(3) Physical function assessment

Grip strength: the grip strength of the dominant hand is measured with an electronic reading table grip strength meter, and the grip distance is adjusted according to the size of the patient's hand. The one-time forced grip strength meter reaches the maximum grip strength value, and the same hand is measured twice with an interval of at least 15s, taking the best one.

Gait speed (GS): walk 4 meters at daily walking speed, time and calculate.

3-meter standing up walking test (TUGT): participants stood up from the chair, walked a distance of 3 meters, and then returned to the sitting position, walking at the daily walking speed.

Five sit up test (FRSST): without using arms (with arms crossed in front of the chest), the time required for the subject to stand up and sit down on a 47cm-tall chair for five consecutive times, counting from the sitting position and ending at the last sitting position.

Simple physical function test (SPPB): it is a comprehensive score, including three parts: the time to walk a distance of 4 meters, the time to complete the FRSST, and the ability to stand in three ways for 10 seconds (with feet, half feet, and full feet).

(4) Activities of daily living (ADL) assessment

Physical self-maintenance scale (PSMS): including 6 items such as toileting, grooming, bathing, eating, dressing, and activities, with a total of 6 points.

The Lawton instrumental activities of daily living (Lawton IADL): 8 items including using transportation, cooking, financial management, making phone calls, taking medicine, washing clothes, shopping and doing housework, with a total of 8 points.

(5) Comorbidity assessment

Charlson comorbidity index and geriatric disease cumulative score scale were used for evaluation. See the attached table for details.

(6) Frailty

Frail debilitating phenotype scale was used.

(7) Medication

Including the quantity and type of medication. The number of medications ≥ 5 was defined as polypharmacy.

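### The divide-by-3 rule in 5.2 gives 667 intervention and 1,333 control (1:2) from numbers 1-2000, not the 500 and 1,500 (1:3) in Section 3

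*Combined protocol and SAP*

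**What the plan says.** Section 3 says that 2,000 people are "randomly assigned to the intervention group (n=500) and control group (n=1500". That accounts for everyone recruited and sets the ratio at 1:3.

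Section 3.1 makes recruitment part of the primary feasibility outcome: more than 2,000 participants, "500 of whom were to be categorized in the intervention group".

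Section 4.1 is looser. Its calculation ends with "a total of 380 individuals were included in the intervention and control groups", after which the project is said to "investigate and follow up with at least 2000 older people and intervene in more than 500 cases".

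Section 5.2 gives the allocation procedure: "A random number table (1-2000 random order) was established", and eligible people receive numbers in the order of that table. The group then depends on the number: "divided by 3 is an integer, and the remaining 1 is the control group, and the remaining 2 is the intervention group". No other section gives an allocation rule, a cap on the intervention arm, or a step that would turn the result of 5.2 into the arm sizes in Section 3.

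**The concern.** Division by 3 sorts the numbers into three nearly equal classes. A rule that assigns whole classes can put about one third or two thirds of the list in an arm, but Section 3 needs one quarter. The two sections therefore describe different trials.

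The allocation ratio and the way it was produced are basic facts of a randomised design. From this plan a reader cannot tell whether the ratio was 1:2 or 1:3. If it was 1:3, the reader cannot tell how that was reached or whether everyone counted as randomised really was. The intervention arm size also enters the feasibility criterion in 3.1.

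**Working it through.** **Inputs.** Numbers 1 to 2000, each used once, and division by 3 (5.2). Arms of 500 and 1,500 (Section 3). Total of 380 over two groups, and more than 500 intervention cases (4.1).

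**The plan's stated figures.** 500 + 1,500 = 2,000; 1,500 / 500 = 3; intervention share 500 / 2,000 = 25%. Section 3 is consistent with itself.

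**Remainder counts.** 2,000 = 3 x 666 + 2. The numbers 1 to 1998 give 666 in each class. Then 1999 leaves remainder 1 and 2000 leaves remainder 2. The counts are 666 (remainder 0), 667 (remainder 1) and 667 (remainder 2). Because the list is fixed, using all of it gives these counts exactly, with no chance variation.

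**Arms under each reading of remainder 0.**

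| Remainder 0 goes to | Intervention | Control | Intervention:control |
|---|---|---|---|
| Control (natural reading) | 667 | 666 + 667 = 1,333 | 1:2 |
| Intervention | 666 + 667 = 1,333 | 667 | 2:1 |
| Neither | 667 | 667 (666 people unassigned) | 1:1 |
| Section 3 | 500 | 1,500 | 1:3 |

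The third reading is unlikely, because Section 3 assigns all 2,000. No row reproduces Section 3.

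**Size of the gap, natural reading.** Intervention: 667 - 500 = +167, and 167 / 500 = +33.4%. Control: 1,333 - 1,500 = -167, and 167 / 1,500 = 11.1% fewer. Intervention share: 667 / 2,000 = 33.35% against 25%.

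**Against the thresholds in 4.1.** 380 / 2 = 190 per group. The smallest arm under any reading is 667, so this is met. More than 500 intervention cases is also met under every reading.

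**Could the rule give 500:1,500 if the intervention arm was closed at 500?** This is an assumption; no section says so. In a random order of 1 to 2000, which holds 667 remainder-2 numbers, the expected position of the 500th of them is 500 x 2001 / 668 = 1,498. About 2,000 - 1,498 = 502 people would follow it (20,000 simulated orders: mean 502, 95% range 450 to 557). All of them would go to control with no chance of intervention, so about 500 of the 1,500 controls would not have been randomised.

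**A divisor that does match Section 3.** 2,000 / 4 = 500 in each of four remainder classes. One class to intervention and three to control gives exactly 500 and 1,500.

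**The case against.** The strongest reply is that nothing is damaged. If 5.2 was followed, a 1:2 allocation is as random as a 1:3 one. Both arms are far above the 190 per group implied by 4.1, and 667 satisfies its figure of more than 500 intervention cases, so 500 can be read as a minimum. This largely stands and is why the point is not rated higher. It does not remove the contradiction: Section 3 also states 1,500 controls out of 2,000, and 1,333 is not 1,500. The reassurance about bias also depends on the rule having been followed, which the text leaves open.

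A second reply is that some other method may have been used. Section 4.1 refers in passing to intervention and control communities, and 4.2 says "The intervention group and the control group were propensity matched", which sits awkwardly with individual randomisation. These are hints only and do not establish another method. If there was one, 5.2 should state it.

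Two smaller points are fair. The totals 667 and 1,333 describe a fully used list of 2,000, whereas 3.1 hopes for more than 2,000 participants; the 1:2 ratio does not depend on this. The closed-arm case is hypothetical and serves only to show why the rule actually used needs stating.

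**Conclusion.** The concern holds. The rule in 5.2 cannot produce the arm sizes in Section 3 under any reading of remainder 0. On the natural reading the intervention arm is 167 larger and the control arm 167 smaller than stated, at 1:2 instead of 1:3. The exact counts assume that all numbers from 1 to 2000 are used; the mismatch in ratio does not rest on that.

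This should be fixed but is not critical. If division by 3 was applied throughout, there is no bias and no shortfall against 4.1. No change in precision is claimed, because 4.2 matches the arms on a propensity score without giving a matching ratio. The documents do not show which section is wrong.

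**What to change.** Make Sections 3, 3.1 and 5.2 agree, and state in 5.2 the group for remainder 0. The wording suggests that allocation has already happened (5.2 says the table was established; 5.1 says "the study was conducted during COVID-19 pandemics period"), although tenses are mixed across the document. The correction should therefore follow what was done:

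- **If division by 3 was used:** keep it, correct Section 3 to about 667 and 1,333 (1:2), and state that the 500 in 3.1 is a minimum. As 3.1 is a primary criterion, date and disclose the change.
- **If 500 and 1,500 were actually reached:** state in 5.2 the rule that produced them. If that was division by 3 with the intervention arm closed at 500, report that anyone assigned to control afterwards was not randomised, and how many there were.
- **Only if allocation has not started:** divide by 4, with one remainder to intervention and three to control. Section 3 then stands as written.

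The cost is a sentence in 5.2 and, if division by 3 was used, corrected figures in Section 3 and a note in 3.1. A look through the existing allocation list is needed only if the arm was closed early.
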